#### 10.2.2 Change in Physical Function (PROMIS Physical Function score)

The endpoint will test whether there is a change in mean PROMIS-29 Physical Function domain scores at 12 months from baseline. Change in PROMIS-29 Physical Function domain score is calculated as:

$$\text{Change in PROMIS-29 Physical Function domain score} = (\text{PROMIS-29 Physical Function domain score at 12-Month} - \text{PROMIS-29 Physical Function domain score at baseline})$$

## Clinical Investigational Plan

Baseline)

The following hypothesis will be tested:

$H_0$ : Change in PROMIS-29 Physical Function domain score  $\leq 0$

$H_1$ : Change in PROMIS-29 Physical Function domain score  $> 0$

The hypothesis will be tested at the 5% significance level. The analysis will be carried out by calculating the 95% LCB on the mean change in PROMIS-29 Physical Function domain score from baseline to 12-month visit based on a t-distribution. If the 95% LCB is greater than 0, the null hypothesis is rejected. The analysis population for this secondary endpoint will include subjects who complete both the baseline and 12-month PROMIS-29 Profile, irrespective of IPG types.

### 10.2.3 Change in Global Health (PROMIS Global Health score)

The endpoint will test whether there is a change in mean PROMIS Global Health Score from baseline to 12 months. Change in PROMIS Global Health Score is calculated as:

Change in PROMIS Global Health Score = (PROMIS Global Health Score at 12-Month – PROMIS Global Health Score at Baseline)

The following hypothesis will be tested:

$H_0$ : Change in PROMIS Global Health Score  $\leq 0$

$H_1$ : Change in PROMIS Global Health Score  $> 0$

The hypothesis will be tested at the 5% significance level. The analysis will be carried out by calculating the 95% LCB on the mean change in PROMIS Global Health Score from baseline to 12-month visit based on a t-distribution. If the 95% LCB is greater than 0, the null hypothesis is rejected. The analysis population for this secondary endpoint will include subjects who complete both baseline and 12-month PROMIS Global Health questionnaire, irrespective of IPG types.

## 10.3 Descriptive Endpoints

The following descriptive endpoints will be reported:

- Proportion of subjects with device, procedure or stimulation-related SAEs and non-SAEs among subjects who receive the permanent implant
- Proportion of subjects who have AEs related to the trial implant procedure among subjects who fail the trial neurostimulator phase
- Summary of procedure-related SAEs and non-SAEs by implanter experience
- Change from baseline to 1, 3, and 6 months post-permanent implant for overall pain intensity measured using the Visual Analog Scale (VAS)
- Change from baseline to 1, 3, and 6 months post-permanent implant for physical function measured using the PROMIS-29 Profile
- Change from baseline to 1, 3, and 6 months post-permanent implant for quality of life measured using the PROMIS Global Health Scale
- Change from baseline to 1, 3, 6 and 12 months post-permanent implant for neuropathic pain measured using the Neuropathic Pain Scale (NPS)

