## Clinical Investigational Plan

	

Change from baseline to 12 months post-permanent implant for quality of life measured using the PROMIS Global Health Scale

Descriptive Endpoints:	
Safety
 

Proportion of subjects with device, procedure or stimulation-related SAEs and non-SAEs among subjects who receive the permanent implant

Proportion of subjects who have AEs related to the trial implant procedure among subjects who fail the trial neurostimulator phase

Summary of procedure-related SAEs and non-SAEs by implant experience

 
Effectiveness
 

Change from baseline to 1, 3, and 6 months post-permanent implant for overall pain intensity measured using the Visual Analog Scale (VAS)

Change from baseline to 1, 3, and 6 months post-permanent implant for physical function measured using the PROMIS-29 Profile

Change from baseline to 1, 3, and 6 months post-permanent implant for quality of life measured using the PROMIS Global Health Scale

Change from baseline to 1, 3, 6 and 12 months post-permanent implant for neuropathic pain measured using the Neuropathic Pain Scale (NPS)

Change from baseline to 1, 3, 6 and 12 months post-permanent implant for sleep disturbance, anxiety, depression, fatigue, ability to participate in social roles and activities, pain interference and pain intensity measured using the PROMIS-29 Profile

Patient Global Impression of Change (PGIC) at 1, 3, 6 and 12 months post-permanent implant

Design:	This study is a prospective, single arm, observational post-approval study. Study follow-ups will occur at 1, 3, 6, and 12 months post-permanent implant.
Devices used:	DRG Neurostimulation System with Axium or Proclaim DRG Implantable Pulse Generator
Study Population	A maximum of 426 adult subjects with moderate to severe chronic, intractable pain of the lower limbs due to CRPS types I and II will undergo a trial of the neurostimulator system at up to 45 study sites in the United States.
Inclusion/Exclusion Criteria	
Inclusion Criteria
 

Subject is male or female <math>\geq</math> 22 and <math>\leq</math> 75 years of age.

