**Clinical Investigational Plan**

at up to 45 centers in the United States. A maximum of 426 subjects will be enrolled to achieve 319 subjects with a permanently implanted system, which will account for expected attrition, to yield 287 subjects for the primary analysis at 12 months post-implant (See Section 10.9 Sample Size for full details). After the last subject with a permanently implanted device reaches the 12-month study visit or crosses the 12-month study visit window, the endpoint analysis will be conducted and reported to the FDA.

After the subject signs the informed consent, s/he will be screened according to the inclusion/exclusion criteria and will undergo a baseline evaluation. Those subjects who meet the criteria for participation will undergo a trial of the DRG Neurostimulation System to assess response to DRG stimulation. Only subjects who report a 50% or greater reduction in overall pain intensity through direct patient-reported percentage of pain relief will receive the permanent implant. Device activation will occur according to the site's standard of care and may occur at the time of permanent system implant. Subjects will then return to the office for follow-up at 1, 3, 6 and 12 months post-permanent implant. Figure 2 below outlines subject flow through the study.

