1.3 Clinical Investigation Design

This study is a prospective, multicenter, single arm, observational, post-approval study with follow-ups at 1, 3, 6 and 12 months post-permanent implant. [REDACTED]

[REDACTED]

[REDACTED]

After the subject signs the informed consent, s/he will be screened according to the inclusion/exclusion criteria and will undergo a baseline evaluation. Those subjects who meet the criteria for participation will undergo a trial of the DRG Neurostimulation System to assess response to DRG stimulation. For purposes of accounting, subjects are considered enrolled in the study only after they receive the trial system implant. Subjects who fail the trial procedure are considered as screen failures. Only subjects who report a 50% or greater reduction in overall pain intensity through direct patient-reported percentage of pain relief at the of trial evaluation period will receive the permanent implant. Device activation will occur according to the site's standard of care and may occur at the time of permanent system implant. Subjects will then return to the office for follow-up at 1, 3, 6 and 12 months post-permanent implant.

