2.3 Endpoint Analysis

2.3.1 Primary Endpoint

The hypothesis is stated as follows:

[REDACTED]

where p is the 12-month serious adverse event rate for subjects who receive the permanent Axium or Proclaim DRG IPG. The hypothesis will be tested at the 5% significance level.

The primary endpoint analysis will be conducted using Kaplan-Meier method on subjects who received the permanent Axium or Proclaim DRG IPG (primary analysis population). The serious adverse events include adverse events which occur after permanent implant and CEC adjudicates as serious events.

The primary endpoint includes all serious adverse events, including ones related to the neurostimulation device or procedure as well as any unrelated serious adverse events.

[REDACTED]

Statistical Analysis Plan

[REDACTED]

[REDACTED]

[REDACTED]

The 12-month (365 days) serious adverse event rate will be estimated using Kaplan-Meier method with a 95% upper confidence bound (UCB) estimated using log-log transformation. If the 95% UCB is less than the [REDACTED], the null hypothesis will be rejected.

[REDACTED]

[REDACTED]

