3.2 Adverse Events

All the adverse device effects, serious adverse device effects, UADEs, USADEs will be summarized for all subjects who enrolled in this trial in terms the number of events, the percentage of subjects with events and event rate as # event/patient-month per CEC adjudication.

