3.5 Descriptive Endpoints or Additional Data

3.5.1 Descriptive endpoints

The following descriptive endpoints will be reported:

Safety

- Proportion of subjects with device, procedure or stimulation-related serious adverse events and non-serious adverse events among subjects who receive the permanent implant
- Proportion of subjects who have adverse events related to the trial implant procedure among subjects who fail the trial neurostimulator phase
- Summary of procedure-related serious adverse events and non-serious adverse events by implanter experience

Effectiveness

- Percent change from baseline to 1, 3, and 6 months post-permanent implant for overall pain intensity measured using the Visual Analog Scale (VAS)
- Change from baseline to 1, 3, and 6 months post-permanent implant for physical function measured using the PROMIS-29 Profile
- Change from baseline to 1, 3, and 6 months post-permanent implant for quality of life measured using the PROMIS Global Health Scale
- Change from baseline to 1, 3, 6 and 12 months post-permanent implant for neuropathic pain measured using the Neuropathic Pain Scale (NPS)
- Change from baseline to 1, 3, 6 and 12 months post-permanent implant for sleep disturbance, anxiety, depression, fatigue, ability to participate in social roles and activities, pain interference and pain intensity measured using the PROMIS-29 Profile
- Patient Global Impression of Change (PGIC) at 1, 3, 6 and 12 months post-permanent implant

The analysis population for these descriptive endpoints will include primary analysis population subjects with available data and no imputation will be implemented.

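### The only endpoint specific to trial-implant-procedure adverse events is computed among trial failures, so no visible output gives that procedure's risk over everyone exposed to it

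*Protocol*

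**What the plan says.** Protocol 10.3 lists, as a descriptive safety endpoint, "Proportion of subjects who have AEs related to the trial implant procedure among subjects who fail the trial neurostimulator phase". The same item stands in Protocol 4.5 and in the list for the annual progress reports in Protocol 10.7. SAP 1.4.3 and 3.5.1 repeat it: "Proportion of subjects who have adverse events related to the trial implant procedure among subjects who fail the trial neurostimulator phase".

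On who is exposed, the Protocol synopsis says that up to 426 adults "will undergo a trial of the neurostimulator system at up to 45 study sites in the United States". Protocol 5.0 gives the planned flow: "A maximum of 426 subjects will be enrolled to achieve 319 subjects with a permanently implanted system", and then "to yield 287 subjects for the primary analysis at 12 months post-implant". SAP 1.3 counts a subject as enrolled once the trial system has been implanted, and adds: "Subjects who fail the trial procedure are considered as screen failures".

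Passing or failing is decided at the end of the system trial, by whether the subject reports at least 50% pain relief (Protocol 8.7). Protocol 9.2 defines procedure-related events as biological reactions to the implant surgery and names pain among the examples.

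Three other reports bear on these events:
- SAP 3.2: adverse device effects, serious and non-serious, "will be summarized for all subjects who enrolled in this trial". SAP 5.0 defines both terms to include procedure-related events.
- Protocol 10.3 and SAP 3.5.1: device-, procedure- or stimulation-related events among permanent-implant recipients, and procedure-related events by implanter experience.
- SAP 2.3.1: the primary endpoint counts "adverse events which occur after permanent implant and CEC adjudicates as serious events".

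Finally, SAP 3.5.1 says that the descriptive endpoints use members of the primary analysis population who have data. SAP 2.3.1 defines that population as recipients of the permanent pulse generator.

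**The concern.** Every enrolled subject undergoes the trial implant procedure, yet the one proportion named for it is taken only in those who later fail. Failure comes after the procedure and turns on reported pain relief. A procedure-related event such as pain or infection could plausibly contribute to it. The denominator may therefore depend on the event being counted, and the proportion in failers need not equal the risk in everyone exposed.

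At stake is whether this safety study can state the risk of the procedure that all its subjects share. Trial-phase events in subjects who go on to a permanent implant are outside the primary endpoint. Where other reports capture them, those reports are not said to distinguish the two procedures. The predecessor randomized study, as summarized in Protocol 2.0, did report the rate of serious events during the system trial separately: 1.3% and 3.9%. With 76 subjects per arm these match 1/76 and 3/76, so the denominators appear to be everyone randomized.

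**Working it through.** **1. Reproduce the planned flow.** The attrition rates are not visible, so I inferred them from the counts in Protocol 5.0.
- 287 / (1 − 0.10) = 318.9, rounded up to 319.
- 319 / (1 − 0.25) = 425.3, rounded up to 426.

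Both match the plan.

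**2. Share of exposed subjects outside the endpoint.**
- Permanent implant: 319 / 426 = 74.9%.
- No permanent implant: 426 − 319 = 107, and 107 / 426 = 25.1%.

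Protocol 8.7 records the reason for not proceeding, so some of the 107 may have passed and stopped for another reason. On the planned counts, 107 is therefore the most that the denominator can hold, and 74.9% is the least that it leaves out.

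**3. What each visible output covers.**

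| Output | Subjects | Trial procedure shown separately? |
|---|---|---|
| Trial-procedure AE endpoint | Trial failures | Yes |
| SAP 3.2 device effects | All enrolled, so all trial-implanted | Not stated |
| Related SAEs and non-SAEs | Permanent-implant recipients | Not stated |
| Procedure-related events by implanter experience | Not limited by phase | Not stated |
| Primary endpoint | Permanent-implant recipients | Trial phase excluded |

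No row combines all exposed subjects with the trial procedure alone.

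**4. Effect of conditioning on failure.** Let r be the overall AE risk, f = 107/426 the proportion failing, and k the relative risk of failing with an AE against without one. If q is the failure risk without an AE, then f = r·k·q + (1 − r)·q, so q = f / (1 + r(k − 1)). Then:
- rate among failers = r·k·q / f = r·k / (1 + r(k − 1));
- share of affected subjects left out = 1 − k·q.

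Neither r nor k is in the documents. With r = 5% assumed:

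| k | Rate among failers | Affected subjects left out |
|---|---|---|
| 1 | 5.0% | 75% |
| 1.5 | 0.075 / 1.025 = 7.3% | 63% |
| 2 | 0.10 / 1.05 = 9.5% | 52% |
| 3 | 0.15 / 1.10 = 13.6% | 32% |

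At k = 2, an overall risk of 2% gives 0.04 / 1.02 = 3.9% among failers, and 10% gives 0.20 / 1.10 = 18.2%. Because the probability of failing given an AE cannot exceed 1, inflation cannot exceed 426 / 107, about fourfold.

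**5. Precision (exact 95% intervals, rate near 5%).**
- 5/107: 1.5% to 10.6%.
- 21/426: 3.1% to 7.4%.

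With no events, the one-sided 95% upper bound is 1 − 0.05^(1/107) = 2.8% against 1 − 0.05^(1/426) = 0.7%.

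**6. Population sentence.** SAP 3.5.1 takes descriptive endpoints in permanent-implant recipients. Trial failures do not receive the permanent implant (SAP 1.3). The intersection is empty, so the endpoint cannot be computed as the SAP is written. Protocol 10.3 asks only for available data and does not have this conflict.

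**The case against.** The strongest reply is that trial-procedure events are not hidden. A reader might infer from the endpoint that they are reported only in failers, or that those of permanent-implant recipients are dropped. The documents do not support either reading. SAP 3.2, read with the enrolment rule in SAP 1.3 and the definitions in SAP 5.0, covers procedure-related events in every trial-implanted subject. The permanent-implant endpoint states no start date that would exclude the trial phase. The restriction to events after permanent implant belongs to the primary endpoint. All of this stands, and it narrows the point to the missing separation of the two procedures.

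Nor does the screen-failure label in SAP 1.3 remove trial failures from the enrolled set. The sentence before it makes trial-system implantation the point of enrolment, and Protocol 7.0 says that trial failures will be accounted for.

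The endpoint is also descriptive, has no hypothesis, and names its own denominator. As a description of failers it is correct. It misleads only if read as the risk of the procedure, and neither document presents it so. That is fair, but the plan then offers no visible figure for the risk.

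The mechanism has limits too. Lead migration is classed as device-related in Protocol 9.2, so it cannot be used as an example of a procedure event causing failure. Pain and infection can, but the documents do not say how often.

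Finally, a table split by phase may exist. SAP 2.2.2 mentions table mockups that are not visible, and SAP 2.1.1, 2.13 and 3.5.2 are redacted. The point is therefore confined to visible text.

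**Conclusion.** The point holds in a limited form. The only endpoint specific to trial-implant-procedure AEs conditions on an outcome observed after the procedure, and it leaves out at least 74.9% of planned exposed subjects (319/426, taking the enrolment maximum as reached). No visible output gives the trial procedure's risk over all who undergo it.

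A reader might go further and conclude that the planned figure will be several times too high. The documents do not support that. If an AE does not affect failure, there is no inflation, although about 75% of affected subjects are still left out. The 5.0% to 13.6% range rests on an assumed 5% risk and assumed relative risks of 1 to 3.

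The empty denominator in SAP 3.5.1 needs no assumption. It follows from the population sentence and the SAP's own definition, and it needs correcting in any case. The primary endpoint and its test are unaffected.

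**What to change.** 1. In Protocol 4.5, 10.3 and 10.7 (with the synopsis) and SAP 1.4.3 and 3.5.1, make the denominator all subjects who receive the trial system. Count trial-procedure-related SAEs and non-SAEs from trial implant up to permanent implant or exit.
2. Keep rows by trial success and failure, so that the figure now planned is still reported.
3. Amend the population sentence in SAP 3.5.1 so that this endpoint uses all trial-implanted subjects rather than the primary analysis population.

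If the mockups or redacted sections already contain a table split by phase, the sponsor need only cite it and make the third change.

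The cost is one changed denominator, a few table rows and one amended sentence. No new data are needed: surveillance starts at consent (Protocol 9.2), and AEs are recorded at trial implant and at the end of the system trial (Protocol synopsis).

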## Clinical Investigational Plan

- Change from baseline to 1, 3, 6 and 12 months post-permanent implant for sleep disturbance, anxiety, depression, fatigue, ability to participate in social roles and activities, pain interference and pain intensity measured using the PROMIS-29 Profile
- Patient Global Impression of Change (PGIC) at 1, 3, 6 and 12 months post-permanent implant

The analysis population for these descriptive endpoints will include subjects with available data.

### 10.4 Additional Data

The following additional data, including but not limited to: percentage of subjects achieving at least a 30% and 50% pain reduction, demographics, paresthesia coverage and intensity, subject satisfaction, programming parameters, implant procedure information, and system information will be summarized and reported.

### 10.5 Sample Size

### 10.6 Subgroup Analysis

Primary and secondary endpoints will be analyzed by comparing subjects who had previously failed SCS for lack of pain relief (i.e. did not receive  $\geq 50\%$  pain relief) to those who had not previously failed SCS (i.e. naïve subjects or those who failed SCS due to reasons other than pain relief).

Primary, secondary and descriptive endpoints will be analyzed for two distinct cohorts based upon the type of IPG received at permanent implant (Axium or Proclaim).

### 10.7 Interim Analysis

There are no planned interim analyses intended to test hypotheses or modify the study. However, the safety endpoints will be descriptively summarized annually in the progress report until the study is closed. The following safety endpoints will be summarized for each interim analysis:

- 12-month SAE rate for permanent implants.
- Proportion of subjects with device, procedure or stimulation-related SAEs and non-SAEs among subjects who receive the permanent implant
- Proportion of subjects who have AEs related to the trial implant procedure among subjects who fail the trial neurostimulator phase
- Summary of procedure-related SAEs and non-SAEs by implanter experience

### 10.8 The Treatment of Missing, Unused, or Spurious Data, Including Drop-Outs and Withdrawals

Analyses of each endpoint will be performed in subjects who provide complete data for each endpoint. Subject accountability for enrolled subjects will be performed prior to analyses of the primary and secondary endpoints. There are no plans to perform imputations for missing data.

## Clinical Investigational Plan

subject dropouts or withdrawals. If spurious data are discovered, these data will be excluded from analyses. Reasons for exclusion of any data from analyses will be summarized.

### 10.9 The Exclusion of Particular Information for the Testing of the Hypothesis

There is no intent to exclude particular information for the testing of hypotheses.

### 11.0 SUBJECT RECRUITMENT

Sites will be provided with IRB-approved laminated cards that list the study inclusion criteria for easy identification of eligible subjects. All sites are expected to develop and implement their own site-specific subject recruitment plan. Study recruitment materials, such as IRB-approved posters and brochures, will be provided to the site upon request.

### 12.0 SUBJECT RELOCATION

If a subject moves from the geographic catchment area of their investigator, then St. Jude Medical (SJM) will first attempt to place the subject with another investigator in the study. If it is not possible to place the subject with another investigator, the subject will be considered lost to follow up per the lost to follow up definition in Section 13 below.

### 13.0 SUBJECT WITHDRAWAL OR DISCONTINUATION

Subjects must be informed about their right to withdraw from the study at any time and for any reason without sanction, penalty or loss of benefits to which the subject is otherwise entitled and withdrawal from the study will not jeopardize their future medical care or relationship with the investigator. Subjects will be asked to specify the reason for the termination, but have the right not to answer.

The subject's future care will not be influenced by a decision, voluntary or otherwise, to withdraw from the study. All reasonable efforts should be made to retain the subject in the clinical study until completion of the study.

Reasons for subject's withdrawal include, but are not limited to:

- Subject refuses to continue participating in the study
- Subject is deceased (cause must be documented)
- Subject's non-compliance
- Subject is 'lost to follow up': Subject does not adhere to the scheduled follow up visits but has not explicitly requested to be withdrawn from the clinical study. Site personnel should at all times make all reasonable efforts to locate and communicate with the subject in order to achieve subject compliance to the scheduled follow up visits:
  1. A subject will be considered 'Lost to Follow Up' after a minimum of 2 phone calls of a physician or delegate at the investigational site to the subject or contact. These 2 phone calls need to be documented in the subject's medical records.

